Liver chemistry threshold stopping criteria have been designed to assure subject safety and to evaluate liver event etiology (in alignment with the US Food and Drug Administration premarketing clinical liver safety guidance).

Study treatment will be stopped if any of the following liver chemistry stopping criteria is met:

1. Alanine aminotransferase (ALT) \square 3x upper limit of normal (ULN) and total bilirubin \square 2xULN (>35% direct bilirubin); or ALT \square 3xULN and international normalized ratio

(INR) \geq 1.5. NOTE: serum bilirubin fractionation should be performed if testing is available. If fractionation is unavailable, urinary bilirubin is to be measured via dipstick (a measurement of direct bilirubin, which would suggest liver injury).

2. ALT \geq 5xULN.
3. ALT \geq 3xULN if associated with symptoms (new or worsening) believed to be related to hepatitis (such as fatigue, nausea, vomiting, right upper quadrant pain or tenderness or jaundice) or believed to be related to hypersensitivity (such as fever, rash or eosinophilia).
4. ALT \geq 3xULN persists for \geq 4 weeks.
5. ALT \geq 3xULN and cannot be monitored weekly for 4 weeks.
6. ALT \geq 5xULN but $<$ 8xULN and labs cannot be monitored weekly for \geq 2 weeks

Subjects with ALT \geq 3xULN and $<$ 5xULN and bilirubin $<$ 2xULN, who do not exhibit hepatitis symptoms or rash, can continue study treatment as long as they can be monitored weekly for 4 weeks.

Concurrent Medication- Prohibited

Subjects who receive concurrent medication or treatment that is prohibited for safety reasons (e.g. live vaccines, cyclophosphamide or B-cell agents such as rituximab) should be withdrawn from study treatment and should not receive additional investigational product without the explicit approval of the Medical Monitor (Funding Sponsor).

Required Actions, Monitoring, and Follow up Assessments following ANY Liver Stopping Event

Actions:

- Immediately discontinue study treatment
- Report the event to GSK within 24 hours

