- Serum acetaminophen adduct HPLC assay (quantifies potential acetaminophen contribution to liver injury in subjects with definite or likely acetaminophen use in the preceding week [James, 2009]). NOTE: not required in China
- Liver imaging (ultrasound, magnetic resonance, or computerised tomography) and /or liver biopsy to evaluate liver disease: complete Liver event case report form

Increased Monitoring Criteria with Continued Therapy

Criteria

- If ALT \geq 5xULN and $<$ 8xULN and bilirubin $<$ 2xULN without symptoms believed to be related to liver injury or hypersensitivity, and who can be monitored weekly for 2 weeks **OR**
- ALT \geq 3xULN and $<$ 5xULN and bilirubin $<$ 2xULN without symptoms believed to be related to liver injury or hypersensitivity, and who can be monitored weekly for 4 weeks

Required Actions

- Notify the GSK medical monitor within 24 hours of learning of the abnormality to discuss subject safety.
- Subject can continue study treatment
- Subject must return weekly for repeat liver chemistries (ALT, AST, alkaline phosphatase, bilirubin) until they resolve, stabilize or return to within baseline

- If at any time subject meets the liver chemistry stopping criteria, proceed as described above for Required Actions and Follow up Assessments following ANY Liver Stopping Event
- If ALT decreases from ALT ≥ 5 xULN and < 8 xULN to ≥ 3 xULN but < 5 xULN, continue to monitor liver chemistries weekly.
- If, after 4 weeks of monitoring, ALT < 3 xULN and bilirubin < 2 xULN, monitor subjects twice monthly until liver chemistries normalize or return to within baseline.

5.1.3 Duration of Treatment and Follow-up.

The above treatment protocol is investigational. However all patients will be treated and monitored according to our standard of care for kidney transplant patients. DSA will be monitored pre-transplant and at 1, 3, 6, 9, and 12 months. We will perform a protocol biopsy at 1 year post-transplant per standard of care.

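### Section 5.1.2 requires belimumab to stop at any ALT ≥5×ULN, yet its continued-therapy list lets some subjects at ≥5× and <8×ULN carry on

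*Combined protocol and SAP*

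**What the plan says.** Section 5.1.2, under Liver Chemistry Stopping Criteria, opens with a mandatory rule: "Study treatment will be stopped if any of the following liver chemistry stopping criteria is met". Six criteria follow. Three matter here.

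- Criterion 2: ALT ≥5×ULN, with no upper limit and no condition on bilirubin, symptoms or monitoring.
- Criterion 5: ALT ≥3×ULN where weekly monitoring for 4 weeks is not possible, also with no upper limit.
- Criterion 6: ALT ≥5×ULN but below "8xULN and labs cannot be monitored weekly for" at least 2 weeks.

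A sentence after the list deals with ALT ≥3× and <5×ULN and bilirubin <2×ULN: subjects "who do not exhibit hepatitis symptoms or rash, can continue study treatment as long as they can be monitored weekly for 4 weeks". The first action after any liver stop is "Immediately discontinue study treatment". Restart needs both permission in the protocol and approval from GSK Medical Governance.

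A later part of the same section, Increased Monitoring Criteria with Continued Therapy, describes two groups. The first has ALT ≥5× and <8×ULN and bilirubin <2×ULN, "without symptoms believed to be related to liver injury or hypersensitivity, and who can be monitored weekly for 2 weeks". The second has ALT ≥3× and <5×ULN with weekly monitoring for 4 weeks. The actions for both include "Subject can continue study treatment", and also: "If at any time subject meets the liver chemistry stopping criteria, proceed as described above for Required Actions and Follow up Assessments". A step-down line begins "If ALT decreases from ALT ≥ 5 xULN and < 8 xULN to ≥ 3 xULN" and asks for weekly liver tests to go on.

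Section 3.6 halts enrollment for review if more than two patients are discontinued for raised liver tests under the protocol's rules.

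**The concern.** One laboratory result falls under two rules that point in different directions. Criterion 2 ends treatment, with restart barred by default. The continued-therapy list names the same subject and allows further infusions. The conditional wording of criterion 6 makes sense only if subjects in this band may otherwise stay on drug, which suggests that text written around an 8×ULN limit was combined with text written around 5×ULN. The documents do not say which limit was intended.

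What is at stake is the dosing of an individual subject. Safety is part of the primary objective, and Section 1.3 states that there is no experience of belimumab with alemtuzumab or tacrolimus. The rule applied also decides whether the subject counts as a liver discontinuation under Section 3.6.

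**Working it through.** The plan states no figure to reproduce: five subjects are enrolled and Section 9 is descriptive. The check is therefore mainly a comparison of the rules.

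**Step 1. Side by side.** Take a first ALT result with bilirubin <2×ULN, no symptoms, weekly monitoring possible, and INR below its stopping level.

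| ALT | Stopping criteria | Continued-therapy list |
|---|---|---|
| ≥3× and <5×ULN | no criterion met | may continue |
| ≥5× and <8×ULN | stop (criterion 2) | may continue |
| ≥8×ULN | stop (criterion 2) | not listed |

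**Step 2. Where the rules clash.** Both sets were coded as logic rules and run over ALT at 3.5, 5, 6, 7.9, 8 and 9×ULN, bilirubin below or above 2×ULN, symptoms no or yes, and weekly monitoring possible or not: 6 × 2 × 2 × 2 = 48 combinations. Three gave a stop under one set and continuation under the other: ALT 5, 6 and 7.9×ULN, each with low bilirubin, no symptoms and monitoring possible. In all three, criterion 2 was the only stopping criterion met. Other subjects in the band stop under the stopping criteria and are not on the continued-therapy list.

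**Step 3. Which rule governs.** The stopping rule is mandatory and any one criterion is enough. The continued-therapy text is permissive, and its return clause applies whenever a stopping criterion is met. Every subject at ≥5×ULN meets criterion 2. Taken literally, the answer is to stop.

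**Step 4. What that leaves.** Whenever criterion 6 is met, criterion 2 is already met, so criterion 6 adds nothing. The first continued-therapy bullet describes only subjects whom criterion 2 has already stopped, so it can never operate.

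**Step 5. Doses affected.** Belimumab is given on Day 0 and at Weeks 2, 4, 8, 12, 16 and 20: 7 doses.

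- Result at the test before the Week 2 dose: 1 dose if stopped, up to 7 if continued. Difference up to 7 − 1 = 6.
- Result at the test before the Week 20 dose: 6 against 7. Difference 1.
- Result after the Week 20 dose: difference 0.

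The gap narrows if criterion 4 (ALT ≥3×ULN for at least 4 weeks) later stops the subject, or if the investigator delays or withholds a dose, as Section 5.1.2 allows.

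**Step 6. Section 3.6.** More than two of five means at least 3 of 5 (3/5 = 60%). Three subjects in this group would add 3 to the liver count under criterion 2. They would add 0 if all continued and met no other liver criterion. The documents give no rate of liver events, so no probability can be attached to this.

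**Step 7. Would raising criterion 2 to ≥8×ULN be enough?** The grid in Step 2 treated monitoring as yes or no, so it cannot show this. Take ALT 6×ULN, bilirubin <2×ULN, no symptoms, weekly monitoring possible for 2 weeks but not 4. Criterion 2 (now ≥8×) is not met and criterion 6 is not met, but criterion 5 is met because it has no upper limit. The subject must stop, while the first continued-therapy bullet still allows continuation. Criterion 5 would also have to be capped at <5×ULN.

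**The case against.** The strongest reply is that the section already settles the overlap. Stopping complies with both parts, since a permission to continue does not oblige anyone to continue, and the return clause points to the stop actions. This stands. A reader might infer that sites are given opposite orders and cannot obey both; the wording does not support that.

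A reader might also count several statements on each side. That does not hold either. The sentence on ALT ≥3× and <5×ULN is silent above 5×ULN. Criterion 6 is itself a stopping criterion, redundant rather than an instruction to continue. The step-down line asks only for weekly tests, which are also required after most liver stops. The direct clash is one mandatory stop against one permission.

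Safeguards exist as well: both branches require contact with GSK within 24 hours. This helps in single cases, but one contact reports a stop already made and the other discusses a subject still on drug, so it does not set the rule.

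What survives is that the protocol names a group as able to continue when its own criteria require that group to stop. Someone who consults only the continued-therapy list could miss this.

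**Conclusion.** The inconsistency is real and the text is wrong as written, but it is confined to the group defined by all four conditions. Read strictly, the ≥5×ULN stop governs. The practical risk is continued dosing by a site that works from the continued-therapy list; the size, 0 to 6 of 7 doses, depends on when the result appears.

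A reader might infer that the enrollment halt is materially compromised. The documents do not support that: three of five subjects would have to be affected, and no event rate is given. Sample size and the descriptive analysis are untouched.

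The statement in Section 5.1.2 that Section 3.5 lists all discontinuation criteria is inaccurate, because Section 3.5 gives no liver threshold. It does cover laboratory abnormalities by investigator judgment, so this is editorial.

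The conclusion rests on the ALT limits in criterion 2 and in the first continued-therapy bullet, both legible. The comparison signs lost from criterion 1 in the PDF reading do not bear on it.

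**What to change.** **Preferred.** Keep ALT ≥5×ULN as an unconditional stop. Delete criterion 6, the first continued-therapy bullet and the step-down line that starts from ≥5× and <8×ULN. This is the cautious choice for an untested combination and matches what the text, read strictly, already requires. Apply it in the meantime.

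**Alternative, only if the sponsor-investigator and GSK confirm that 8×ULN was intended.**

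- Change criterion 2 to ALT ≥8×ULN.
- Cap criterion 5 at <5×ULN.
- Extend the continuation sentence after the stopping criteria to ≥5× and <8×ULN with weekly monitoring for 2 weeks.
- State the action if ALT is still ≥5×ULN after 2 weeks. Persistence alone would otherwise trigger a stop only under criterion 4, at 4 weeks.

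In either case, say in Section 3.6 that the liver count uses the criteria of Section 5.1.2, and reword the cross-reference to Section 3.5 so that it does not claim to be complete.

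**Cost.** A protocol amendment with IRB approval. Under the preferred fix, some subjects without symptoms stop belimumab earlier than the continued-therapy list would have allowed. No visits or tests are added, because Section 7 already plans hepatic tests before each treatment cycle, and the analysis does not change.

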3.6 Criteria for Terminating the Study

The Principal Investigator will review safety and efficacy criteria on an ongoing basis. The study enrollment will be halted and data reviewed by the Data Safety Monitoring Committee and the University of Wisconsin Health Sciences Institutional Review Board for any of the following:

- 1) If greater than two patients are discontinued from study treatment due to elevated liver function tests as described in the protocol.
- 2) If greater than two patients develop hypogammaglobulinemia and infectious complications resulting in discontinuation of study treatment
- 3) Death of one or more patients.

After this review, the Investigator, Data Safety Monitoring Committee and the IRB will jointly make a final determination regarding continuation, modification, or termination of the study. The study can be terminated at any time for any reason by the Principle Investigator or GlaxoSmithKline, Inc. Should this be necessary, the patient should be seen as soon as possible. The investigator may be informed of additional procedures to be followed in order to ensure that adequate consideration is given to the protection of the patient's interests. The investigator will be responsible for informing the DMC, IRB and the FDA of the early termination of the trial.

See Section 7.3 for information on the ICTR Data Monitoring Committee (DMC) for this study.

4. Selection of Subjects

Potential subjects will be identified prior to kidney transplant based on the following inclusion and exclusion criteria.

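### Section 5.1.2: the liver stopping list and the continuation sentence below it disagree for hypersensitivity signs other than rash, in a narrow set of subjects

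*Combined protocol and SAP*

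**What the plan says.** Section 5.1.2, under the liver chemistry stopping criteria, opens its list with a mandatory instruction: "Study treatment will be stopped if any of the following liver chemistry stopping criteria is met". Six items follow.

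Item 3 applies from ALT 3xULN, with no upper ALT limit and no bilirubin condition. It is met by new or worsening symptoms of either of two kinds: those "believed to be related to hepatitis (such as fatigue, nausea, vomiting, right upper quadrant pain or tenderness or jaundice", or those "believed to be related to hypersensitivity (such as fever, rash or eosinophilia".

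After item 6 comes a permissive sentence for subjects with ALT 3 to <5xULN and bilirubin <2xULN. It says that those "who do not exhibit hepatitis symptoms or rash, can continue study treatment as long as they can be monitored weekly for 4 weeks".

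Later in Section 5.1.2, under increased monitoring with continued therapy, the rule for the same ALT and bilirubin range is stated again. This time it covers subjects "without symptoms believed to be related to liver injury or hypersensitivity, and who can be monitored weekly for 4 weeks". The required actions there add: "If at any time subject meets the liver chemistry stopping criteria, proceed as described above".

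Section 3.6 halts enrollment for review on several grounds. The first is: "If greater than two patients are discontinued from study treatment due to elevated liver function tests as described in the protocol".

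**The concern.** Stopping and continuing should be complements: a subject who meets a stopping item should not also qualify to continue. Here the symptom conditions do not match. Item 3 covers any sign attributed to hypersensitivity and gives three examples. The continuation sentence keeps the hepatitis symptoms but reduces the hypersensitivity side to rash. Fever and eosinophilia are absent from it, and they are not among item 3's hepatitis examples either, so they are not excluded by that route.

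The gap is not tied to those two signs. Sections 1.1 and 1.3 list myalgia, headache and facial edema among delayed hypersensitivity reactions to belimumab. None of these is rash, and none is among item 3's hepatitis examples.

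The two paths differ in practice. A liver stopping event brings immediate discontinuation, a report to GSK within 24 hours, repeat chemistries and follow-up assessments (within 24 to 72 hours where no bilirubin or INR criterion is involved), and no rechallenge without GSK governance approval. Continuing brings notification of the medical monitor, weekly chemistries and further dosing.

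**Working it through.** The plan has no figure to reproduce for this point. The check is to put one subject through each rule, then change one feature at a time.

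**Test subject:** ALT 3 to <5xULN; bilirubin <2xULN; no other stopping item met (for example INR below 1.5); weekly monitoring possible; no hepatitis symptoms; no rash; new fever or eosinophilia that the investigator attributes to hypersensitivity.

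| Case | Stopping list | Sentence after item 6 | Increased-monitoring criterion | Stopping list and sentence conflict? |
|---|---|---|---|---|
| Test subject | Stop (item 3) | May continue | Not eligible to continue | **Yes** |
| Same, plus rash attributed to hypersensitivity | Stop (item 3) | Not eligible | Not eligible | No |
| Same, plus hepatitis symptoms | Stop (item 3) | Not eligible | Not eligible | No |
| Same, but bilirubin at or above 2xULN | Stop (item 3) | Not eligible | Not eligible | No |
| Same, but weekly monitoring not possible | Stop (items 3 and 5) | Not eligible | Not eligible | No |
| Same, but fever attributed to another cause and no other sign | Item 3 not met | May continue | May continue | No |

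The conflict appears only in the first row. It needs every one of the listed conditions, including the investigator's attribution to hypersensitivity.

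**Does the text say which rule wins?** For this ALT range, the increased-monitoring criterion matches both limbs of item 3 and sends anyone who meets a stopping item back to the stopping actions. That favors the stopping list. But Section 5.1.2 states no order of precedence, and the list cannot simply be assumed to prevail throughout. Item 2 stops treatment at ALT 5xULN, yet the increased-monitoring text allows continuation from 5 to <8xULN under conditions, and item 6 has an independent role only if item 2 is not absolute.

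**Link to the Section 3.6 halt.** More than two discontinuations means at least three of the five planned subjects (3/5 = 60%). One subject is 1/5 = 20% of the trial and one of the three discontinuations needed. The wording would change the halt only if exactly two other subjects had already been discontinued for liver tests and the next fell in the narrow set above.

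**The case against.** The strongest reply is that the protocol, read as a whole, already resolves the matter. The stopping list is mandatory, while the later sentence is permissive and does not claim to override an item already met. The mention of hepatitis symptoms and rash can be read as shorthand for item 3's two limbs. The increased-monitoring criterion agrees with item 3 and refers back to it. Section 5.1.2 also requires discussion with the medical monitor within 24 hours and lets the investigator delay or withhold a dose. Section 3.5 requires discontinuation where the investigator sees a significant safety risk. No endpoint or analysis is touched, since Section 9 is descriptive only.

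Much of this stands. It makes the problem a wording conflict with limited practical reach. It does not remove it: the sentence sits directly under the stopping list that staff would consult, the shorthand reading is not stated, and a call to the medical monitor does not say which text governs.

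Four stronger readings are tempting, and the documents do not support them:

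- **That every subject in this ALT and bilirubin range with fever or eosinophilia and no rash is affected.** Item 3 needs attribution to hepatitis or hypersensitivity, and several such subjects are treated alike by both texts, as the table shows.
- **That the increased-monitoring text is a third, conflicting rule for ALT 3 to <5xULN.** Its wording differs, but it agrees with item 3.
- **That the combination is likely because fever is common.** Section 1.3 lists fever as an alemtuzumab infusion reaction and pyrexia among belimumab reactions at 5% or more. Neither is a rate for fever attributed to hypersensitivity together with ALT at or above 3xULN.
- **That the Section 3.6 halt is materially compromised.** The effect needs two prior liver discontinuations and then this particular case.

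**Conclusion.** The inconsistency is real and narrow. For one definable type of subject, item 3 requires a stop and the sentence after item 6 permits continuation. The matching criterion under increased monitoring sides with item 3, which limits the ambiguity without removing the conflicting sentence.

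The size cannot be expressed as a rate, because the documents give no frequency for the combination. The figure of 20% is one subject's share of a five-subject trial and not a probability. The effect on the Section 3.6 halt is secondary.

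The conclusion rests on reading the symptom words of the continuation sentence as written, and on fever and eosinophilia not counting as hepatitis symptoms, which follows item 3's own examples. It is worth correcting because a patient-safety rule should not contradict itself and the correction is cheap.

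**What to change.** Reconcile item 3, the continuation sentence after item 6 and the increased-monitoring criterion for ALT 3 to <5xULN, so that a single symptom definition governs both stopping and continuing. Defining the symptoms once and referring to that definition in the other two places would do it. Which clinical rule should apply is for the sponsor and investigator to decide.

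Section 3.6 needs no separate change: its halt already counts liver discontinuations as the protocol defines them, so it will follow the reconciled text.

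The cost is about one sentence in an amendment, with no extra data or visits.

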- Complete the liver event CRF and complete SAE data collection tool if the event also meets the criteria for an SAE (All events of ALT \geq 3xULN and bilirubin \geq 2xULN ($>35\%$ direct bilirubin) or ALT \geq 3xULN and INR >1.5 , if INR measured which may indicate severe liver injury (possible 'Hys Law'), must be reported as an SAE (excluding studies of hepatic impairment or cirrhosis); INR measurement is not required and the threshold value stated will not apply to subjects receiving anticoagulants)
- Perform liver event follow up assessments
- Monitor the subject until liver chemistries resolve, stabilize, or return to within baseline (see MONITORING below)
- Do not restart/rechallenge subject with study treatment unless allowed per protocol and GSK Medical Governance approval is granted **Monitoring:**

For bilirubin or INR criteria:

- Repeat liver chemistries (include ALT, AST, alkaline phosphatase, bilirubin) and perform liver event follow up assessments within **24 hrs**

- Monitor subjects twice weekly until liver chemistries resolve, stabilize or return to within baseline
- A specialist or hepatology consultation is recommended For All other criteria:
- Repeat liver chemistries (include ALT, AST, alkaline phosphatase, bilirubin) and perform liver event follow up assessments within 24-72 hrs
- Monitor subjects weekly until liver chemistries resolve, stabilize or return to within baseline

Follow Up Assessments:

- Viral hepatitis serology (Includes: Hepatitis A IgM antibody; Hepatitis B surface antigen and Hepatitis B Core Antibody (IgM); Hepatitis C RNA; Cytomegalovirus IgM antibody; Epstein-Barr viral capsid antigen IgM antibody (or if unavailable, obtain heterophile antibody or monospot testing); Hepatitis E IgM antibody) Serum creatine phosphokinase (CPK) and lactate dehydrogenase (LDH).
- Fractionate bilirubin, if total bilirubin \geq 2xULN
- Obtain complete blood count with differential to assess eosinophilia
- Record the appearance or worsening of clinical symptoms of liver injury, or hypersensitivity, on the AE report form
- Record use of concomitant medications on the concomitant medications report form including acetaminophen, herbal remedies, other over the counter medications
- Record alcohol use on the liver event case report form For bilirubin or INR criteria:
- Anti-nuclear antibody, anti-smooth muscle antibody, Type 1 anti-liver kidney microsomal antibodies, and quantitative total immunoglobulin G (IgG or gamma globulins).

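### Liver stopping criterion 1 includes an INR limb, but no INR is required in a subject who continues belimumab with ALT of 3 to <5xULN; a reflex INR would be a cheap safety improvement

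*Combined protocol and SAP*

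**What the plan says.** All the relevant rules are in Section 5.1.2.

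- **Stopping rule.** The lead sentence is mandatory: "Study treatment will be stopped if any of the following liver chemistry stopping criteria is met". Criterion 1 has two limbs, both needing ALT of at least 3xULN. One adds raised total bilirubin. The other reads "3xULN and international normalized ratio" with a threshold of at least 1.5. The note to criterion 1 says what to do if bilirubin fractionation is unavailable. It says nothing about an INR that has not been drawn.
- **Continuation rule.** Subjects with ALT of 3 to <5xULN and bilirubin <2xULN "who do not exhibit hepatitis symptoms or rash, can continue study treatment as long as they can be monitored weekly for 4 weeks". The increased-monitoring text repeats this and sets the weekly tests: "Subject must return weekly for repeat liver chemistries (ALT, AST, alkaline phosphatase, bilirubin) until they resolve, stabilize or return to within baseline". It also says that the stopping criteria go on applying throughout.
- **SAE reporting.** For the same ALT and INR combination, the bullet under required actions after a stopping event is conditional: "if INR measured which may indicate severe liver injury". It adds: "INR measurement is not required and the threshold value stated will not apply to subjects receiving anticoagulants". Here the INR threshold is above 1.5, not at least 1.5.
- **Repeat tests after a stop.** "Repeat liver chemistries (include ALT, AST, alkaline phosphatase, bilirubin) and perform liver event follow up assessments within" 24 hours for the bilirubin or INR criteria. INR is not named here either.

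Elsewhere, the Section 6.1 screening liver tests are AST, ALT and total bilirubin. Appendix A has no INR or coagulation row. Section 7 calls for hepatic function tests before each treatment cycle without listing them.

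**The concern.** A mandatory stopping rule can only work if the quantity it depends on is measured. Here one limb of criterion 1 depends on a test that the protocol does not ask for, in the very subjects who are allowed to go on receiving the drug with raised ALT.

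The protocol itself says that this combination may signal severe liver injury. Section 1.3 says there is no experience of belimumab combined with alemtuzumab or tacrolimus. INR status also decides how closely a stopped subject is followed. The bilirubin or INR branch calls for repeat tests within 24 hours and monitoring twice a week; the other criteria allow 24 to 72 hours and weekly monitoring. What is at stake is the safety of an individual subject, not the interpretation of the trial.

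**Working it through.** The protocol gives no figure to reproduce on this point. The check has two parts: a comparison of the rules, and a count of the doses that could fall in the gap. Some comparison signs in the criteria list are damaged in the text; I read the ALT signs as at or above, which agrees with the intact ones.

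**1. Can a subject meet the stop and also every written condition for continuing?** Take two hypothetical subjects who differ only in INR.

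| | Subject A | Subject B |
|---|---|---|
| ALT | 4xULN | 4xULN |
| Bilirubin | normal | normal |
| Symptoms or rash | none | none |
| Weekly monitoring possible | yes | yes |
| True INR | 1.0 | 1.6 |
| Meets criterion 1 | no | **yes** (INR limb) |
| Meets criteria 2, 3, 5 or 6 | no | no |
| Meets written conditions for continuing | yes | **yes** |

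The four weekly tests cannot tell A from B. Criterion 4 (ALT of at least 3xULN persisting for at least 4 weeks) would eventually stop both.

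**2. Is an INR required anywhere else?**

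| Source | INR named? | Leaves room for INR? |
|---|---|---|
| 5.1.2 weekly tests while continuing | no | no, four tests listed |
| 5.1.2 repeat tests after a stop | no | yes, the list is introduced by *include* |
| 5.1.2 discretionary repeat tests | no | yes |
| 6.1 screening labs | no | yes, the standard-of-care list is not exhaustive |
| 6.3.3 monthly standard-of-care labs | no | yes |
| 7 hepatic function tests before each cycle | no | yes, not itemised |
| Appendix A | no | metabolic panel not itemised |

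Several sources permit an INR. None requires one.

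**3. How many doses could fall in the gap?** Doses are at Weeks 0, 2, 4, 8, 12, 16 and 20, that is Days 0, 14, 28, 56, 84, 112 and 140. If raised ALT is first seen on Day t and persists, count the doses on Day d with t < d < t + 28, the period before criterion 4 applies.

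- Week 1 (t = 7): 7 < d < 35 gives Days 14 and 28, so 2 doses.
- Week 2 (t = 14): 14 < d < 42 gives Day 28, so 1 dose.
- Week 4 (t = 28): 28 < d < 56 gives none. Weeks 8, 12 and 16 have the same 28-day gap and also give 0. No dose follows Week 20.

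Two sensitivities:

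- **Visit windows.** Section 6.3 states ±3 days for Week 1, and Appendix A prints 3 days with a damaged sign for the later dosing visits. Assuming ±3 days, a 28-day gap can shrink to 28 − 6 = 22 days, so the maximum becomes 1 at Weeks 4 to 16.
- **Detection between visits.** Raised ALT first seen on a standard-of-care test between dosing visits, from Day 29 to Day 139, leaves 1 nominal dose inside 28 days.

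A dose given at the detection visit itself would add 1 if the result were not back before the infusion. The documents do not say whether it would be.

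**4. Do the two INR thresholds agree?** No. An INR of exactly 1.5 meets criterion 1 but not the SAE bullet. The anticoagulant exemption appears only in the SAE bullet, so criterion 1 as written would also stop a subject whose INR is raised by an anticoagulant.

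**The case against.** The strongest reply is that the protocol has already decided the matter. Its only statement on whether INR must be drawn says that it need not be. Criterion 1 can be read consistently with that: it says what to do if INR is found to be raised, and does not order the test. INR is also a coagulation test, so its absence from a list of liver chemistries is unsurprising. This stands as a plausible account of intent. It does not close the gap, because it confirms that one limb of a mandatory stop is left to chance.

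It is also fair to say that the dose counts include doses which the protocol properly allows in subjects with a normal INR. They show that dosing can occur before criterion 4 applies, and nothing about how often a stop would be missed.

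The remaining safeguards are real: weekly bilirubin, the stops for symptoms, persistence and inability to monitor, the option to delay or withhold a dose, and prompt contact with the company: "Notify the GSK medical monitor within 24 hours of learning of the abnormality to discuss subject safety".

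A reader might infer two stronger things. One is that the protocol would let a subject with a known raised INR continue. It would not: any one criterion stops treatment, and the increased-monitoring text says that the stopping criteria still govern. The other is that INR will not be measured in this trial. The documents do not show that either, since discretionary and standard-of-care testing could supply it.

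**Conclusion.** The point holds as an optional, low-cost improvement to patient safety. As written, staff who follow the protocol exactly can dose a subject who meets criterion 1, because nothing requires the INR that would reveal it.

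The exposure is bounded. On the nominal schedule it is at most 2 further doses if raised ALT is first seen at Week 1, or 1 at Week 2, before the persistence rule applies. This assumes that ALT stays in the 3 to <5xULN band, bilirubin stays <2xULN, no symptoms appear and weekly monitoring is kept up. The frequency cannot be estimated: the documents give no rate of raised ALT or of raised INR, and only 5 subjects are planned. No endpoint or analysis changes, so the dose counts should not be read as expected harm.

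The finding is confined to ALT of 3 to <5xULN because criterion 2 stops treatment at 5xULN. The increased-monitoring text also appears to allow continuation at 5 to <8xULN; that is a separate inconsistency.

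**What to change.** Make three changes in Section 5.1.2.

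1. **Increased monitoring with continued therapy.** Add INR to the repeat tests for any subject with ALT of at least 3xULN who is not receiving anticoagulants, and require the result to be reviewed before the next belimumab dose.
2. **SAE bullet and criterion 1.** Replace the statement that INR need not be measured with a requirement to measure it at ALT of at least 3xULN unless the subject is anticoagulated. Carry the anticoagulant exemption into criterion 1.
3. **Threshold.** Use one INR cut-off in both places, either at least 1.5 or above 1.5.

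The review-before-next-dose wording belongs only in the continued-therapy text. Subjects under the stopping-event actions have already come off treatment. No INR is needed routinely when ALT is below 3xULN.

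Adding only an if-measured qualifier to criterion 1 would align the wording but change nothing for the subject.

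The cost is a wording amendment, one extra assay at a draw already required, and an occasional stop for an INR raised for a non-hepatic reason.
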